3.2 Responsibility for Analyses/In-House Blinding

The statistical analysis of the data obtained from this study will be the responsibility of the Clinical Biostatistics Department of the Sponsor.

The Sponsor will generate the randomized allocation schedule(s) for study treatment assignment for this protocol, and the randomization will be implemented in IRT.

Part 1 of this trial will be conducted as a double-blind trial under in-house blinding procedures. Blinded sponsor personnel will remain blinded throughout study conduct and the official, final database will not be unblinded until medical/scientific review has been performed, protocol deviations have been identified, and data have been declared final and complete. In addition, the site radiologist(s) will perform the imaging review without knowledge of treatment group assignment and provide their results to the site investigator.

Blinding with respect to planned efficacy interim analyses is described in Section 3.7 – Interim Analyses. Protocol-specified blinding to treatment assignment will be maintained at all investigational sites.

Part 2 of this trial is open-label, so individuals participating in Part 2 will not remain blinded throughout the entire conduct of the trial.

3.3 Hypotheses/Estimation

3.3.1 Primary Objective(s) and Hypothesis(es)

Objective: To compare Recurrence-free Survival (RFS) between treatment arms.

Hypothesis: Pembrolizumab is superior to placebo with respect to RFS as assessed by the site investigator.

3.3.2 Secondary Objective(s) & Hypothesis(es)

1) **Objective:** To compare DMFS between treatment arms.

Hypothesis: Pembrolizumab is superior to placebo with respect to DMFS as assessed by the site investigator.

2) **Objective:** To compare OS between treatment arms.

Hypothesis: Pembrolizumab is superior to placebo with respect to OS.

3) **Objective:** To assess the safety and tolerability of pembrolizumab compared to placebo in the proportion of AEs.

3.3.3 Exploratory Objectives

- 1) **Objective:** To compare average change from baseline during the adjuvant treatment period (up to 21 days after last administration) in global quality of life between the 2 treatment arms using the European Organization for Research and Treatment of Cancer Quality of Life Questionnaire (EORTC QLQ-C30) global health status/QoL scale.
- 2) **Objective:** To compare average change from baseline after the adjuvant period (from 21 days after last administration) in global quality of life between the 2 treatment arms using the EORTC QLQ-C30 global health status/QoL scale.
- 3) **Objective:** To characterize health utilities using the EuroQoL-5 Dimension Questionnaire (EQ-5D-5L) healthy utility scores.
- 4) **Objective:** To compare the time to subsequent therapy (TTST) between treatment arms.
- 5) **Objective:** To compare Progression/recurrence-free Survival 2 (PRFS2) between treatment arms.
- 6) **Objective:** To identify molecular (genomic, metabolic, and/or proteomic) biomarkers that may be indicative of clinical response/resistance, safety, pharmacodynamic activity, and/or the mechanism of action of pembrolizumab.

3.4 Analysis Endpoints

3.4.1 Efficacy Endpoints

3.4.1.1 Primary Efficacy Endpoint

Recurrence-free Survival (RFS)

Recurrence-free Survival is defined as the time from randomization to any of the following events: recurrence of melanoma at any site (local, in-transit or regional lymph nodes or distant recurrence) or death due to any cause. New incident cases of melanoma and second cancer diagnoses are not counted as events for recurrence-free survival. RFS analysis will be done for Part 1.

3.4.1.2 Secondary Efficacy Endpoints

Distant Metastasis-free Survival (DMFS)

Distant Metastasis-free Survival is defined as the time from randomization to the first diagnosis of a distant metastasis. Distant metastasis refers to cancer that has spread from the original (primary) tumor and beyond local tissues and lymph nodes to distant organs or distant lymph nodes.

Overall Survival (OS)

Overall survival is defined as the time from randomization to death due to any cause.

3.4.1.3 Tertiary/Exploratory Efficacy Endpoints

Time to Subsequent Therapy (TTST)

Time to subsequent therapy is defined as time from randomization to the date of first subsequent therapy (eg, surgery, radiation therapy, antineoplastic therapy) or death (whatever the cause) whichever occurs first.

Progression-free survival 2 (PRFS2)

Progression/recurrence-free Survival 2 is defined as the time between the date of randomization and the earliest of the following:

- date of 1st disease progression per RECIST1.1 beyond the initial unresectable disease recurrence (unresectable local-regional disease recurrence or unresectable distant metastatic disease recurrence);
- date of 2nd recurrence in Participants without evidence of disease after surgery of a resectable 1st recurrence (resectable local regional recurrences or resectable distant metastatic disease recurrence);
- date of death.

3.4.1.4 Exploratory Endpoints Associated with Protocol Part 2

Progression-Free Survival

Progression-free survival (PFS) is defined as the time from the date of 1st dose in Part 2 to the first documented disease progression or death due to any cause, whichever occurs first.

The following analyses will be done for Part 2.

- PFS per RECIST 1.1 assessed by investigators
- PFS per iRECIST assessed by investigators.

Objective response rate

Objective response rate (ORR) is defined as the proportion of the participants in the analysis population who have a confirmed complete response (CR) or partial response (PR).

The following analyses will be done for Part 2.

- ORR per RECIST 1.1 assessed by investigators
- ORR per iRECIST assessed by investigators.

Duration of Overall Response (DOR)

For participants who demonstrated CR or PR, response duration is defined as the time from first documented evidence of CR or PR until disease progression or death due to any cause, whichever occurs first.

The following analyses will be done for Part 2.

- DOR per RECIST 1.1 assessed by investigators
- DOR per iRECIST assessed by investigators.

Overall Survival (OS)

For Part 2, overall survival is defined as the time from the date of 1st dose in Part 2 to death due to any cause.

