
 
Objective: To compare average change from baseline after the adjuvant period (from 21 days after last administration) in global quality of life between the 2 treatment arms using the EORTC QLQ-C30 global health status/QoL scale
 
	
 
EORTC QLQ-C30 global health status/QoL scale.
 

 
Objective: To characterize health utilities using the EuroQoL-5 Dimension Questionnaire (EQ-5D-5L) healthy utility scores.
 
	
 
EQ-5D-5L health utility score.
 

 
Objective: to compare the time to subsequent therapy (TTST) between treatment arms
 
	
 
TTST: The time from randomization to the date of first subsequent therapy (eg, surgery, radiation therapy, antineoplastic therapy) or death (whatever the cause), whichever occurs first.
 

 
Objective: to compare Progression/recurrence-free Survival 2 (PRFS2) between treatment arms
 
	
 
PRFS2: Time from randomization to the earliest of the following: (1) date of 1st disease progression per RECIST 1.1 beyond the initial unresectable disease recurrence; (2) date of 2nd recurrence in patients without evidence of disease after surgery of a resectable 1st recurrence; (3) death.
 

 
Objective: To identify molecular (genomic, metabolic, and/or proteomic) biomarkers that may be indicative of clinical response/resistance, safety, pharmacodynamic activity, and/or the mechanism of action of pembrolizumab.
 
	
 
Germline genetic variation, genetic deoxyribonucleic acid (DNA) mutations from tumor, tumor and blood RNA variation, proteomics and immunohistochemistry (IHC), and other biomarkers.
 

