The imaging schedule for participants with local, surgically resected recurrence will be every 12 weeks during treatment. Investigators will assess recurrence radiographically (with site radiologist) and/or by examination with subsequent biopsy during treatment and follow-up. Lesions identified by physical examination should be photographed and submitted to the imaging vendor. For participants with unresectable local (regional metastatic lymph nodes, in-transit, satellite, and/or micrometastases) or distant recurrence imaging will also be every 12 weeks during treatment. Investigators will use RECIST 1.1/iRECIST to assess disease response/progression for participants entering Part 2 therapy with unresectable/metastatic disease.

Follow-up visits and imaging schedules will be scheduled in Part 1 and Part 2 per the SoA (Section 1.3).

Detailed information on Parts 1 and 2 is found in Section 8.

The primary endpoint of the study is RFS. Secondary endpoints include DMFS and OS. Distant metastasis refers to cancer that has spread from the original (primary) tumor and beyond local or nearby tissues and lymph nodes to distant organs or distant lymph nodes. This study will also examine the safety and tolerability of adult or pediatric pembrolizumab doses administered every 3 weeks for 17 cycles and at recurrence for 17 or 35 cycles as a secondary endpoint. Safety evaluations will include AE monitoring, physical examinations, clinical laboratory parameters (hematology and chemistry), vital signs, and assessment of ECOG, KPS or LPS (Appendix 8: Performance Status Scales). Adverse events will be monitored throughout the study and graded in severity according to the guidelines outlined in the NCI CTCAE Version 4.0.

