All eligibility criteria from Part 1 Sections 5.1 and 5.2 remain valid and must be reconfirmed prior to enrollment into Part 2 of the study with the EXCEPTION of:

- Inclusion Criteria 2, 3, 4 and 5
- Exclusion Criteria 5, 6 and 11

Participants must also meet the following requirements for entry into Part 2:

- Participant must have experienced an investigator determined/confirmed disease recurrence radiographically and/or by exam with subsequent biopsy. Local recurrence must be documented with photo image. Participants will only be eligible for Part 2 treatment after the first recurrence. If a participant experiences a second recurrence, they will not be eligible for Part 2. Participants who are less than 6 months from their last Part 1 pembrolizumab dose at the time of recurrence are not eligible for Part 2 treatment.

Note: Cutaneous lesions and other superficial lesions detectable only by physical exam must be categorized as nontarget lesions for Part 2 of the study.

- No new anticancer treatment was administered after the last dose of Part 1 study treatment.
- Participant is continuing from Part 1 and has completed 17 cycles of pembrolizumab or any number of cycles with placebo with no delays in treatment  $\geq 12$  weeks. If a  $\geq 12$ -week treatment delay has occurred, Sponsor approval must be obtained before moving into Part 2 of the study.

Note: For any participant who is not able to complete the required 17 cycles of pembrolizumab or have  $\geq 12$ -week treatment delay on placebo arm, a notification to the Sponsor is required to determine if it would impact their eligibility for entry into Part 2.

- Surgical resection or biopsy of unresectable or metastatic disease completed within 4 weeks of first dose.

- Full resection of lesions or biopsy of unresectable or metastatic disease confirmed by site pathologist to be melanoma.

Note: If biopsy is clinically contraindicated, investigators should seek Sponsor review and approval to start participant on Part 2 therapy.

If participant is identified to have a thoracic lesion or lymph node suspicious for a recurrence (especially if solitary lesion), it is encouraged that a biopsy be performed to confirm metastatic melanoma versus another lung primary malignancy versus a nonmalignant lung disease (eg, sarcoidosis).

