Objective response should be confirmed by a repeat scan assessment. Tumor scans to confirm PR or CR should be performed at least 4 weeks after the first indication of a response is observed. Participants will then return to regular scheduled scans, starting with the next scheduled scan time point. Participants who receive additional imaging for confirmation do not need to undergo the next scheduled tumor scan if it is less than 4 weeks later; tumor scans may resume at the subsequent scheduled imaging time point.

Response assessment in Part 2 will be based on RECIST 1.1/ iRECIST as assessed by investigator/local radiology review. Objective response to confirm PR/CR is based on RECIST 1.1, and iRECIST will be used to confirm PD after initial site-assessed radiologic PD per RECIST 1.1 in clinically stable participants. Per iRECIST (Section 8.2.1.5), disease progression should be confirmed by the site 4 to 8 weeks after site-assessed first radiologic evidence of PD in clinically stable participants. Participants with unconfirmed disease progression may continue on treatment at the discretion of the investigator until disease progression is confirmed by the site, provided they have met the conditions detailed in Section 8.2.1.5. Participants who receive confirmatory scans do not need to undergo the next scheduled tumor scan if it is less than 4 weeks later; tumor scans may resume at the subsequent scheduled scan time point, if clinically stable. Participants with confirmed disease progression by iRECIST, as assessed by the site, will discontinue study treatment. Exceptions are detailed in Section 8.2.1.5.

A central imaging vendor will be used to collect, clean, and hold tumor scans. Images will be collected for possible analysis by BICR. The same scan technique should be used at each time point and the schedule of disease assessment should not be adjusted for delays, if any, in cycle starts of disease assessment. The process for scan collection and transmission to the central imaging vendor can be found in the Site Imaging Manual (SIM).

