#### **8.11.3.4 Survival Follow-up Contacts**

Part 1 participants with distant metastases will move into Survival Follow-up if they do not qualify for or choose to not enter Part 2 of the study. Part 2 participants with a history of distant metastases or who develop new distant metastases during Part 2 will move into Survival Follow-up.

Participant Survival Follow-up status will be assessed approximately every 12 weeks until death, withdrawal of consent, or the end of the study, whichever occurs first. The collection of survival includes disease status (recurrence, progression, or new malignancy) if available or not already collected in imaging scans; record of further anticancer therapies and the outcomes in accordance with local regulations and participant consent.

The first Survival Follow-up assessment should be scheduled as described below:

- For participants who discontinue treatment intervention and who will not enter the efficacy follow-up phase, the first Survival Follow-up contact will be scheduled 12 weeks after the discontinuation visit and/or Safety Follow-up visit (whichever is last).
- For participants who completed assessments in Efficacy Follow-up, the first Survival Follow-up contact will be scheduled 12 weeks after the last Efficacy Follow-up visit has been performed.

These participants should be assessed or contacted by telephone or at an in-person visit approximately every 12 weeks to review disease status, recent imaging, and current therapy. Site investigator must collect and review copy of imaging reports, photographs, and pathology reports (including imaging and biopsy/pathology assessment done external to site) to update disease status if it is available. A central imaging vendor will be used to collect, clean, and hold submitted tumor imaging obtained during the SFU phase of the study. In the event that a participant refuses any further contact, or if a participant is discontinued from the study, the participant can authorize their site investigator to provide updated information about their tumor, anticancer treatment, well-being, and overall status updates on their behalf.

Radiographic imaging in Survival Follow-up may be performed as clinically indicated, per local standard of care, or following new anticancer therapy imaging schedule. Information regarding poststudy anticancer treatment will be collected if new treatment is initiated.

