3.6.1.5 Progression-free survival 2 (PRFS2)

The non-parametric Kaplan-Meier method will be used to estimate the distribution for PRFS2. 95% CIs for the median and point estimates at various follow-up times from randomization date will be calculated. Participants who remain alive and whose disease has not recurred, or disease has recurred, but subsequent disease progression or recurrence has not occurred, will be censored on the date of last disease assessments.

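### After an unresectable first recurrence, PRFS2 counts only RECIST 1.1 progression or death, but RECIST assessment is set out only for Part 2, which early pembrolizumab-arm recurrences cannot enter

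*SAP*

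**What the plan says.** **Endpoint.** Protocol Section 3 gives the objective as "Objective: to compare Progression/recurrence-free Survival 2 (PRFS2) between treatment arms", and SAP 3.3.3 repeats it. PRFS2 runs from randomization to the earliest of three events (SAP 3.4.1.3; Protocol 9.4.1.3):

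- after an unresectable first recurrence, the "date of 1st disease progression per RECIST1.1 beyond the initial unresectable disease recurrence";
- after a resected first recurrence, the "date of 2nd recurrence in Participants without evidence of disease after surgery of a resectable 1st recurrence";
- death.

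**Where RECIST applies.** Protocol 4.1: "Investigators will use RECIST 1.1/iRECIST to assess disease response/progression for participants entering Part 2 therapy with unresectable/metastatic disease". Protocol 8.2.1.2: "Response assessment in Part 2 will be based on RECIST 1.1/ iRECIST as assessed by investigator/local radiology review". The 12-weekly scan schedule in 8.2.1.2 and 8.2.1.4.2 is counted from the first Part 2 dose. Protocol 8.2.1.5 makes RECIST 1.1 the main measure of progression without naming a Part, but gives no baseline or schedule outside Part 2.

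**Who may enter Part 2.** Protocol 6.7 offers crossover to placebo participants who recur at any time and meet the other criteria. For the other arm: "Participants who are less than 6 months from their last Part 1 pembrolizumab dose at the time of recurrence are not eligible for Part 2". Pembrolizumab-arm participants who stopped Part 1 treatment because of recurrence are also excluded.

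**Follow-up outside Part 2.** Protocol scans stop on entry to DMFS or Survival Follow-up (8.2.1.2), and later scans follow local care or the schedule of a new therapy (8.2.1.4.1). Survival Follow-up records "disease status (recurrence, progression, or new malignancy) if available" (8.11.3.4).

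**Analysis.** SAP 3.6.1 continues PRFS2 follow-up whether or not Part 2 is entered. Participants alive whose disease has recurred, "but subsequent disease progression or recurrence has not occurred, will be censored on the date of last disease assessments" (SAP 3.6.1.5).

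**The concern.** A comparison from randomization needs the event to be looked for in the same way in both arms. Here one limb of the endpoint depends on an assessment method tied to Part 2, and the door to Part 2 opens differently by arm. A placebo participant with an unresectable recurrence in month 10 can cross over and have RECIST scans every 12 weeks. A pembrolizumab participant with the same recurrence cannot, and goes to a follow-up phase with local scans and no RECIST requirement.

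If progression in the second participant is found late, or is not counted because it was not assessed by RECIST, the record shows a later event or a censored time. That would lengthen apparent PRFS2 on pembrolizumab. The arm-specific curves would still be read as the comparison the objective promises.

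**Working it through.** **Step 1. Reproduce the plan's RFS event counts.** PRFS2 has no stated event count or power, so the RFS model serves only to size the barred group. Inputs from Protocol 9.9.1: control RFS 68% at 60 months and 50% long-term; HR 0.60; 16-month enrollment; 4.7% yearly drop-out. There are 954/2 = 477 participants per arm.

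- λ = −ln[(0.68 − 0.50)/(1 − 0.50)]/60 = −ln(0.36)/60 = 0.01703 per month
- Placebo S₀(t) = 0.5 + 0.5·exp(−0.01703t); pembrolizumab S₁(t) = S₀(t)^0.6
- Drop-out rate η = −ln(1 − 0.047)/12 = 0.00401 per month
- Events by study month T = 477 × ∫ f(t)·exp(−ηt)·min[1, (T − t)/16] dt, where f is the event density of the arm

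| Month | Placebo | Pembrolizumab | Total | Plan |
|---|---|---|---|---|
| 33 | 78.4 | 48.8 | 127.2 | 128 |
| 48 | 109.4 | 69.3 | 178.7 | 179 |

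The model matches the plan.

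**Step 2. Length of the barred window.** Cycle 17 starts 16 × 21 = 336 days after the first dose. Adding 6 months (182.6 days) gives 518.6 days, and 518.6/30.44 = 17.0 months. This assumes that all 17 doses are given on schedule and that dosing starts at randomization.

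**Step 3. Events in the window.** Pembrolizumab-arm first RFS events up to month 17 from randomization: 35.7.

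- Share of those expected by month 48: 35.7/69.3 = 52%. By month 33: 35.7/48.8 = 73%.
- With the window ending at 16.5 to 18 months, and with either this cure model or the form 0.5^(1 − exp(−θt)), the month-48 share runs from 34.8/69.3 = 50% to 39.7/70.8 = 56%.
- Placebo events barred on timing: 0 of 109.4.

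**Step 4. Narrow to the RECIST limb.** The 36 events include deaths and resectable recurrences. The documents do not give the unresectable share. If it were 25%, 50% or 75% of these events (assumed), about 9, 18 or 27 participants would be affected.

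**Step 5. Illustration of direction only.** Simulated with assumed medians of 9 months from first to second event, then 24 (or 12) months to death, analyzed at month 60, window 17 months. A missed second event is replaced by death. With no missed events the PRFS2 HR is about 0.60. Suppose half of the recurrences are unresectable and half of the second events in those barred participants are missed:

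- HR about 0.56 (0.58 with 12 months to death);
- if 30% in both arms also do not enter Part 2 and have the same gap, about 0.57–0.58 (0.59).

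The medians, capture rates, unresectable share and non-entry rate are not in the documents. The SAP would also censor living participants at the last assessment, which this simulation does not do.

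**The case against.** The case against a strong version is good, and most of it stands.

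- **RECIST governs one limb of three.** A reader might infer that PRFS2 as a whole needs RECIST. It does not: second recurrence after resection and death are free of it.
- **Detection outside Part 2 is not absent.** A reader might infer that death is the only event that can be captured for barred participants. But Protocol 8.11.3.3 and 8.11.3.4 provide for contacts about every 12 weeks that review disease status, imaging and therapy. The Part 1 schedule requires investigators in DMFS follow-up to collect and review reports. SAP 3.6.1 keeps PRFS2 follow-up open. What is missing is a scan schedule and a stated way to date progression.
- **The gap is not confined to one arm.** Part 2 is optional, and other exclusions apply to both arms, so placebo non-entrants are followed in the same way.
- **No PRFS2 hazard ratio or test is specified.** SAP 3.6.1.5 plans Kaplan-Meier estimates with confidence intervals, and the endpoint is exploratory with no alpha. Nor do the documents call PRFS2 the test of adjuvant treatment against treatment at recurrence; they say only that the arms are to be compared.

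These points reduce the size and certainty of the problem but do not remove it. Continuing follow-up without a method still leaves the unresectable limb defined by an assessment that the protocol describes only for Part 2.

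**Conclusion.** The concern holds in a limited form. As written, the unresectable limb of PRFS2 relies on assessments that are less available to the pembrolizumab arm because of a timing rule that applies only to that arm. About half of that arm's expected first RFS events by month 48 (about 36 of 69, range 50–56%) fall in the barred window. This rests on the protocol's RFS assumptions, proportional hazards at 0.60 and full on-schedule dosing. The number affected through RECIST is smaller and unknown.

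The likely direction is in favor of pembrolizumab, but the documents do not establish that second events will be missed, or how many. A reader might conclude that the PRFS2 comparison is biased by a known amount; any such figure depends on assumed capture rates and event times. The imbalance is one of degree. RFS is unaffected, because its event is the first recurrence or death, before Part 2 begins. This is a cheap improvement to an exploratory endpoint.

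**What to change.** 1. In SAP 3.4.1.3 and 3.6.1.5, date progression after an unresectable first recurrence by the earliest investigator-documented progression by any method (imaging, examination or pathology), whether or not the participant entered Part 2.
2. Present the RECIST 1.1-only version as a sensitivity analysis.
3. Record the date of progression or second recurrence at the existing 12-weekly DMFS and Survival Follow-up contacts.
4. Report by arm how many first recurrences were followed in Part 2, in DMFS follow-up and in Survival Follow-up.

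Do not add start of second-line therapy as a PRFS2 event. It would change the endpoint and add a discretionary trigger after unblinding.

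Protocol Section 9 allows changes to exploratory analyses to be documented in the supplemental SAP before any analysis is run. The main cost is therefore a change of definition and recording a date at contacts where sites already review disease status. The downside is a slightly less standardized progression date. No treatment or eligibility rule changes.
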